3.1 Study setting

The study will take place at public schools in Moss municipality, Norway, and pupils in grades 5 to 10 (aged 10-16 years) will be invited to participate.

3.2 Eligibility criteria

In Moss municipality, all public schools will be included in the study, except one school for pupils with special needs, a setting which makes it impossible to study the effects of the intervention in a comparable way.

3.3 Intervention

Our intervention, *5Ways@School*, will be based on the *Five Ways to Wellbeing* programme, which is a set of evidence-based public mental health messages aimed at improving the mental health and wellbeing of the whole population. The *Five Ways* promote five dimensions of activities, each of them being associated with mental health and quality of life; making up a «mental health literacy tool box» (Aked et al., 2008). They were developed by the New Economics Foundation in the UK, and the *Five Ways to Wellbeing* programme is currently being used for adults in Norwegian Healthy Lifestyle Centres. Several studies have been conducted, examining potential benefits of the *Five Ways* and similar interventions (Mackay et al., 2019), and two studies are currently being conducted in Norway among adult populations (Eilertsen, 2020; Prydz, 2021). To our knowledge, there is no previous research on the *Five Ways* in Norwegian children or adolescents.

The *5Ways@School* intervention will be a teaching material consisting of five elements; Take notice, Be active, Keep Learning, Connect, and Give. The intervention will be given in an ordinary classroom setting by the class's main teacher in two school hours of 45 minutes each week for six consecutive weeks, i.e., a total of 12 school hours. The teaching sessions will consist of presentations of the five elements, videos, reflection exercises, focused group discussions, creative group work, and giving the pupils small "challenges" to practice what they have learned between the weekly sessions.

Prior to the intervention, the teachers will attend a whole day seminar where they will learn the scientific background of the intervention, the intervention manual will be presented, and any questions responded to. They will receive a copy of the intervention manual one week before this seminar. School nurses, social teachers, and other school personnel will also be given this seminar, so that they may use the same five elements in their follow-up of individual pupils who need extra support.

To avoid potentially confounding effects from other health promoting initiatives, the municipality will not promote the implementation of other, similar interventions or teaching materials during the study period and follow-up period, so that any effect we detect should be attributable to the *5Ways@School* intervention. However, some teachers might choose to use other teaching material on their own initiative, like UNICEF's recently available "Sammen og aktiv med mening (SAM)" (Eng.: "Together and active with meaning"). We have investigated whether the participating schools are currently using other health promoting programmes, and found that one school is currently using one such programme, called "Robust Youth 12–16", which is aimed at "Strengthening the individual's robustness and class environments and school cultures where all are included" (*Robust Youth 12–16*, 2022). The school in question will continue using the "Robust Youth 12–16" programme during the study period, and we will take this into account when analysing the data: We

will ask the participating pupils whether they have had the teaching material "SAM" or "Robust Youths" so that we can investigate possible interaction or confounding effects.

When publishing our results, we will report sufficient details of our intervention to allow replication.,

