The purpose of the current study is to develop an evidence-based, health-promoting intervention and investigate its effects on well-being and mental health among school pupils aged 10 to 16 in Moss municipality, Norway.

In the first phase of the study, we will pilot the intervention at two selected schools in Råde municipality. In the second phase of the study, we will run a full-scale trial at the public schools in Moss (16 schools; approximately 3,300 pupils). For the latter purpose, we will use the quasi-experimental Extended Selection Cohorts design. We will investigate the changes in the pupils' scores on health behaviours, mental health, and well-being from baseline to different timepoints of data collection during a 12 months follow-up period.

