3.4.8 Pupils' knowledge of other health promoting programs

Pupils will be asked whether their class/school has completed one of the following teaching programs: 1) SAM, and 2) Robust Youths. Response options are "yes" and "no".

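### Exposure to Robust Youth in the one school known to use it is to be handled only through a pupil yes/no item, and the SAP has no term or sensitivity analysis for it

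*Combined protocol and SAP*

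**What the plan says.** Section 3.3 (Intervention) says that the sponsor checked which other programmes the schools use and "found that one school is currently using one such programme". The programme is Robust Youth 12–16. The school will go on with the "programme during the study period, and we will take this into account when analysing the data". The means given is that the sponsor "will ask the participating pupils whether they have had the teaching material" SAM or Robust Youth, "so that we can investigate possible interaction or confounding effects". SAM is a different case, because "some teachers might choose to use other teaching material on their own initiative".

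Section 3.4.8 gives the item: "Pupils will be asked whether their class/school has completed one of the following teaching programs", namely SAM and Robust Youth. The answers are yes or no, with no option for pupils who do not know.

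Section 3.11 (Statistical Analysis Plan) sets out a multilevel model with school as the top level and lists the moderators to be explored. Neither programme is among them, neither is named as a covariate, and no analysis without the known school is planned. Section 4.5 says that school name and class membership will be left out of the final dataset.

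**The concern.** The sponsor already knows which school uses Robust Youth, yet the plan relies on the recall of pupils aged 10 to 16. The item invites error in both directions. An exposed pupil may answer 'no' because it asks about completion and the programme is still running. An unexposed pupil who is unsure has to guess, at a time when life skills is a topic at every school level. When true exposure is rare, wrong 'yes' answers from the many unexposed schools can rival or outnumber the true ones.

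The second difficulty is attribution. With one known exposed school, a difference in intervention effect between exposed and unexposed pupils is close to a difference between that school and the other 15.

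At stake is whether the commitment in section 3.3 can be kept. Adjusting for a poorly measured exposure removes only part of any confounding, and a reported interaction could reflect one school's character or reporting error.

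**Working it through.** **Inputs from the documents.** Section 2.1 gives "16 schools; approximately 3,300 pupils". Section 3.7 gives about 2,300 expected participants, 15 per class, 157 classes, intra-class correlation 0.05, effect size 0.16 and a two-sided 5% level. Section 3.3 gives one known user school.

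**Assumptions.** Schools are of equal size and the whole user school is exposed. The documents give no sensitivity or false-'yes' rate for the item, so a range is used.

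**The plan's own figure.** The plan has no figure on this point, but its power figure confirms the clustering inputs used in step 3. The non-centrality is √[157 × 0.16² / (4 × (0.05 + 0.95/15))] = √(4.019/0.4533) = 2.98. With 155 degrees of freedom the power is 0.8411, as stated. The design effect is 1 + 14 × 0.05 = 1.70.

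**Step 1: share of 'yes' answers that are true.** The exposed share is 1/16 = 6.25%, or 2,300/16 ≈ 144 pupils. With sensitivity *se* and false-'yes' rate *f*:

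PPV = se × (1/16) / [se × (1/16) + f × (15/16)]

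| f | PPV, se 0.70 | PPV, se 0.80 | PPV, se 0.90 |
|---|---|---|---|
| 0% | 1.00 | 1.00 | 1.00 |
| 1% | 0.82 | 0.84 | 0.86 |
| 2% | 0.70 | 0.73 | 0.75 |
| 5% | 0.48 | 0.52 | 0.55 |
| 10% | 0.32 | 0.35 | 0.38 |

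For example, at se 0.80 and f 5% there are 0.80 × 143.75 = 115 true and 0.05 × 2,156.25 ≈ 108 false 'yes' answers, and 115/223 = 0.52.

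A crude contrast between 'yes' and 'no' pupils shrinks by the factor PPV + NPV − 1, if errors are unrelated to the outcome. At se 0.80 this is 0.99, 0.83, 0.71, 0.50 and 0.33 down the rows.

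**Step 2: other exposed shares, at se 0.80 and f 5%.** If only half of the school is exposed (1/32), PPV is 0.025/(0.025 + 0.0484) = 0.34. If the school is large and holds 1/8 of pupils, PPV is 0.10/(0.10 + 0.04375) = 0.70.

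**Step 3: one school against 15.** Suppose true intervention effects vary between schools with SD τ, Robust Youth makes no difference, and the analysis ignores this variation. A rough standard error for one school's before–after effect is √(2 × 1.70/143.75) = 0.154, which ignores the correlation between a pupil's own repeated answers. The real size of a nominal 5% two-sided test is 2 × [1 − Φ(1.96 × √(0.154²/(0.154² + τ²)))]. For assumed τ of 0.05, 0.10 and 0.20 this gives about 6%, 10% and 23%.

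**Step 4: reach into the main contrasts.** At 12 months (section 2.3) exposed cohorts are compared with unexposed same-grade cohorts from the same schools. A programme that ran before baseline and continues is largely common to both sides. The February contrast compares different schools. With about half of 16 schools in each group, the user school is about 1/8 of its group. If Robust Youth moved that school's scores by 0.16 SD (borrowing the plan's effect size purely for scale), the group mean would move by 0.16/8 = 0.02 SD.

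**The case against.** The strongest reply is that the documents show no misclassification. They give no error rates. At 1% false positives more than 80% of 'yes' answers are true, and a large user school would raise the share. That stands: a reader might infer that the variable is mostly wrong, but the documents do not establish it.

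A reader might also infer that the plan contains an interaction test that should be dropped. It does not. Section 3.3 speaks only of looking into interaction or confounding, and section 3.11 defines no such test. The gap that can be documented is that the intention never reaches the SAP.

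Nor do the documents say that Robust Youth will be confined to one school throughout. They report what was found at planning. Asking pupils everywhere could pick up later adoption, and it could pick up SAM, for which there is no list of schools. The item therefore has a use, and since it asks about the class or school, its answers could be summarised by class.

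Finally, it would be too absolute to say that no interaction can be estimated. The programme's name refers to ages 12–16 while the study covers 10–16, and its coverage within the school is not stated. Some within-school contrast may exist.

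None of this explains why a school-level fact already in hand should be replaced by recall, or why the SAP is silent. The school level in the model does not by itself cure the attribution problem, because no intervention effect varying by school is stated.

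**Conclusion.** The point holds as a minor one. The plan names a known exposed school, proposes to allow for it only through a pupil item that is open to error, and carries nothing into the SAP. The item's reliability could range from nearly perfect to poor, depending on false-'yes' rates that the documents do not give and on the size and grade coverage of the school. Any apparent interaction with Robust Youth would be hard to attribute to the programme rather than to that school, unless coverage is partial.

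The main results are little affected. About 1/16 of the sample is involved if schools are of equal size, and the February wait-list contrast is the more exposed of the two. The limited effect on the 12-month comparison assumes that the programme covers the same grades in both years. Section 4.5 adds a practical obstacle. Read literally, it would leave the pupil item as the only marker of exposure and make it impossible to set the known school aside, although the model in section 3.11 needs school and class in any case.

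**What to change.** - Define Robust Youth exposure from the school's own record, by class or grade if coverage is partial, and update it during the study.
- Pre-specify in section 3.11 the main contrasts with and without that school, the February contrast above all.
- State that any Robust Youth interaction is descriptive only.
- Keep the pupil item as a supplementary check for SAM and for later adoption, summarised by class.
- Retain coded school and class identifiers in the analysis dataset, and reconcile section 4.5 with the multilevel model in section 3.11.

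The cost is some SAP wording, a short record from the schools, and one sensitivity analysis that drops about 1/16 of the sample. The coded identifiers add nothing that the planned model does not already need.

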3.4 Outcomes

3.4.1 Subjective wellbeing

As a measure of *present* global life satisfaction, a version of the Cantril Ladder Scale will be used, one that has been used in the Young in Norway study (Cantril, 1965). Pupils are asked to evaluate their life at the present time, on a scale from 0 (feeling very poor) to 10 (feeling very well).

As a measure of expected *future* global life satisfaction, pupils are asked to estimate how good or bad their life will be in five years from now, on the Cantril Ladder Scale.

Satisfaction with different life domains will be measured by asking the pupils "how satisfied are you with the following aspects of your life: your parents, your friends, your school, your neighborhood, your health, and your appearance?". Pupils respond to each item on a four-point scale ranging from "not at all" to "very satisfied".

3.4.2 Social relationships

Relationships with friends will be assessed by asking the pupils: "Do you have a friend whom you can trust and talk to about everything?", with response options "Yes, I am sure", "Yes, I think so", "I don't think so", and "I have no friends, nowadays".

The pupils will be asked two items; "Do you have [a friend] to be with during 1) your leisure time and 2) in the school breaks?" These items will be measured by a four-point scale ranging from "Yes, always" to "No, never".

3.4.3 Loneliness

Loneliness will be assessed by one item on feelings of loneliness in the past week, on a four-point scale from 'affected not at all' to 'affected extremely'.

3.4.4 Mental health

Depressive symptoms will be measured by Kandel and Davies's six-item Depressive Mood Inventory (Kandel & Davies, 1982). This measure was derived from the widely used Hopkins Symptom Checklist (Derogatis et al., 1974) and assesses depressive symptoms during the preceding week on a four-point scale from 'affected not at all' to 'affected extremely'. The scale has been shown to correlate highly with other measures of adolescent depressive symptoms in Norway (von Soest & Wichstrøm, 2014). In addition to this instruments, we will use the five prosocial items from the Strengths and Difficulties Questionnaire (SDQ), a validated instrument that has been used in Norway before (Goodman et al., 1998; Sagatun et al., 2008).

3.4.5 Leisure activities and screen time

The respondents' weekly leisure activities will be assessed with the following items: "In your leisure time, how often do you 1) meet with friends in their homes, 2) hang out with friends [outdoor], 3) exercise or do sports, 4) ride a horse, 5) stay at a youth activity club, 6) play an instrument, 7) do things together with your family, 8) help at home doing chores, 9) relax on your own most of the evening". The pupils will respond on a six-point scale ranging from "never" to "every day".

The respondents' daily leisure activities and screen time will be assessed with the following items: "In your leisure time, how many hours a day do you 1) watch tv, tv series, and/or YouTube, 2) read

books, 3) play computer games, 4) play games on your smartphone, 5) use social media, 6) read/watch news". The pupils will respond on a six-point scale ranging from "no time" to "3 hours or more".

3.4.6 Indicators of socio-economic status

Family socio-economic status will be assessed by a composite score four items from Family Affluence Scale II (Currie et al., 2008; Currie et al., 1997), which include frequency of traveling for family holidays in the previous year, number of computers and cars in the family, and having an individual room at home. The scale ranges from 0 to 9, where a low score indicates low socio-economic status.

3.4.7 Other demographics

Gender will be assessed. Only school grade (grades 5 to 10) but not age will be assessed. In the Norwegian school system, attendance in school grades is strictly organized by birth cohorts, and staying back (repeating a grade) due to poor academic performance is generally not practised. We therefore use school grade as an indicator of age.

The pupils will be asked whether both their parents are born in a country other than Norway, and whether they have one or two homes.

3.4.8 Pupils' knowledge of other health promoting programs

Pupils will be asked whether their class/school has completed one of the following teaching programs: 1) SAM, and 2) Robust Youths. Response options are "yes" and "no".

3.4.9 Data on feasibility and acceptability

The teachers who will be teaching the interventions will be asked: "Based on your experiences, which of the five elements in the 5Ways@School do you think was 1) most useful for the pupils?, easiest for you to teach, and 3) most challenging for you to teach? The teachers will respond to these questions by choosing any of the five elements of the 5Ways@School: Take notice, Be active, Keep Learning, Connect, and Give.

The teachers will respond on a four-point scale from "agree completely" to "disagree completely" to the following items: 1) I was well motivated to teach the 5Ways@School, 2) I enjoyed teaching the 5Ways@School, 3) Teaching life skills through the 5Ways@School is a natural part of my job as a teacher, 4) I got sufficient information and/or training before I started teaching the 5Ways@School, 5) I think the pupils learned something new and useful, 6) There was too little activities in the 5Ways@School, 7) There was too much activities in the 5Ways@School, 8) I followed the teaching manual to a high degree, 9) I completed all the six lessons in the 5Ways@School, 10) I had to abbreviate one or more lesson(s), 11) I think that the 5Ways@School should be part of the ordinary school curriculum in 5h to 7th grade, and 12) I think that the 5Ways@School should be part of the ordinary school curriculum in 8th to 10th grade.

We will also investigate the experiences of school nurses, school leaders, and parents through focus group interviews.

Participating pupils will be given a questionnaire with the following items: 1) I enjoyed learning about 5Ways@School, 2) I learned something new, that I can make use of, 3) The teaching was easy to understand, 4) The teaching was boring, 5) The teaching was interesting, 6) There was too little activities, 7) There was too much activities, 8) The teaching made me sad, afraid, or angry, 9) The teaching made me happy, 10) I will practise more of the five ways in the future, 11) I think all pupils should learn about the five ways. The pupils will respond on a four-point scale from "agree completely" to "disagree completely".

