2.2 Objectives

Our objectives are:

1. To adapt the existing *Five ways to wellbeing* course for adults to a school setting, and to pilot the intervention in two schools.
2. To explore how participating pupils, teachers, and other school personnel experience the pilot intervention, and identify aspects that should be adjusted before proceeding to a full scale trial.
3. To examine how the teachers deliver the intervention in the full scale trial; their motivation, obstacles they encounter, general satisfaction with the intervention, and their adherence to the intervention manual (i.e., fidelity).
4. To investigate whether the intervention is acceptable and experienced as useful for participating school pupils, parents, teachers, and other school personnel.
5. To investigate whether the intervention have any adverse effects, such as triggering negative emotions.
6. To evaluate the process of implementation.
7. To describe the pupils' wellbeing and mental health at baseline (November 2023).

8. To examine the immediate and long-term effects of the intervention on the pupils' wellbeing and mental health.
9. To assess for whom the intervention is effective (i.e., subgroup analysis and moderation analysis, for example SES, gender, baseline symptom levels, etc.).
10. To investigate what mechanisms explain potential improvements in wellbeing after exposure to the interventions.

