3.8 Recruitment

The teaching programme will take place at school, during ordinary teaching hours. The Head of education in Moss municipality has decided to use the teaching programme in the interdisciplinary topic of public health and life skills for all pupils in 5th to 10th grade. All pupils in these grades will consequently be exposed to the teaching programme. All pupils in 5th to 10th grade in the public schools in Moss will be invited to complete questionnaires, except pupils attending a special education school (N=18).

Teachers who deliver the intervention will be invited to complete questionnaires.

Some teachers, school nurses, school leaders, and parents will be invited to participate in focus group interviews.

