4.5 Confidentiality

The participants' confidentiality will be protected by strict procedures, ensuring that personal information will be de-identified. By de-identified, we refer to data where personal identifying information is removed. To prevent the possibility of data re-identification, school name and school class membership will not be included in the final dataset (only gender and school grade). Data will not be disclosed to others or transferred to countries outside of Norway.

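### Teacher items 9 and 10 record no quantity, so halving every lesson can give the same answers as halving one, and the fidelity objective gets no estimate of the amount delivered

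*Combined protocol and SAP*

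**What the plan says.** **The planned amount.** Section 3.3 gives the teaching as "two school hours of 45 minutes each week for six consecutive weeks, i.e., a total of 12 school hours". It also says that pupils get small tasks to "practice what they have learned between the weekly sessions", so the teaching is organised week by week. The protocol does not define the word lesson.

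**The objective.** Objective 3 in section 2.2 covers how teachers deliver the programme, including "their adherence to the intervention manual (i.e., fidelity".

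**The measure.** Section 3.4.9 introduces the teacher statements with "The teachers will respond on a four-point scale from 'agree completely' to 'disagree completely' to the following items". Three of the twelve concern delivery: item 8, "I followed the teaching manual to a high degree", and items 9 and 10, "I completed all the six lessons in the 5Ways@School, 10) I had to abbreviate one or more lesson(s". None asks for a count.

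**Other sources.** No teaching log or classroom observation is described. On focus groups, section 3.8 says: "Some teachers, school nurses, school leaders, and parents will be invited to participate in focus group interviews". Section 4.5 adds that "school name and school class membership will not be included in the final dataset (only gender and school grade".

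**The concern.** How much of the programme was taught is a matter of fact, but items 9 and 10 collect it as a degree of agreement. Item 10 also has its threshold at a single shortened lesson. A teacher who shortened one lesson and a teacher who shortened all six can both agree fully and truthfully, and both can also agree that all six lessons were completed. An intermediate answer to either item does not correspond to any number of lessons.

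What is at stake is the reading of the result. Ordinary class teachers deliver the programme in school time, and section 3.7 assumes an effect of only 0.16. If the observed effect is null or small, the first question will be whether the programme does little or was not fully taught. Item 10 shows that shortening was foreseen, but its answers cannot show how much took place.

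**Working it through.** **Inputs.** From section 3.3: 2 school hours a week, 45 minutes each, 6 weeks. From section 3.4.9: the wording of items 8 to 10. Assumption: one lesson is one weekly session of two school hours (90 minutes). This fits section 3.3 but is not stated there.

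**The plan's own figure.** 2 × 6 = 12 school hours, as stated. 12 × 45 = 540 minutes. Under the assumption, 6 lessons × 90 = 540 minutes, so six lessons and 12 school hours agree.

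**Answers implied by a literal reading of items 9 and 10**

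| Delivery | Minutes | Share of 540 | Item 9 (all six completed) | Item 10 (any shortened) |
|---|---|---|---|---|
| Six lessons in full | 6 × 90 = 540 | 100% | agree | disagree |
| One lesson halved | 45 + 5 × 90 = 495 | 92% | agree | agree |
| Every lesson halved | 6 × 45 = 270 | 50% | agree | agree |
| Three dropped, three in full | 3 × 90 = 270 | 50% | disagree | disagree |

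With k lessons halved, the time delivered is 540 − 45k minutes. For k = 1 to 6 this is 495, 450, 405, 360, 315 and 270 minutes, that is 92%, 83%, 75%, 67%, 58% and 50%. All six cases give the pattern in the second and third rows. The last row has the same 50% but a different pattern, so the overlap is specific to shortening.

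**Why delivery matters for the effect (illustration only).** The power in section 3.7 is reproduced with J = 157 classes, n = 15 pupils per class, effect f = 0.16, intra-class correlation 0.05 and two-sided 0.05. The noncentrality is √[J f² / (4 × 0.05 + 4 × 0.95/15)] = √(4.0192/0.4533) = 2.98 on 155 degrees of freedom. This gives power 0.8411, as stated.

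Now assume, without support in the documents, that the effect is proportional to teaching time and that a share q of classes received half. The mean effect is 0.16 × (1 − 0.5q):

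| q | Mean effect | Power |
|---|---|---|
| 10% | 0.152 | 0.80 |
| 25% | 0.140 | 0.735 |
| 50% | 0.120 | 0.60 |
| 100% | 0.080 | 0.32 |

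Any such loss would come from delivery and not from the questionnaire. The point is only that items 9 and 10 could not show which row applies if the time was lost by shortening.

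**The case against.** A reader might infer three stronger points that the documents do not support.

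- *Six lessons contradicts 12 school hours.* It does not. Six weekly sessions of two school hours make 12. The weakness is only that lesson is undefined in the protocol. The manual and the training seminar may define it for teachers, but neither is available for review.
- *Half the teaching can never be told apart from nearly all of it.* Half the time lost by dropping three lessons should appear as disagreement with item 9. That answer would still not say how many lessons were dropped.
- *The plan has no fidelity measure.* It has some. Item 8 addresses adherence to the manual directly, which is how objective 3 describes fidelity. Items 9 and 10 give the shares of teachers reporting full completion and any shortening.

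The defence can add that a teacher who halved every lesson has reason to score item 8 lower, and perhaps item 10 higher, than one who shortened a single lesson. Focus groups and the process evaluation (objective 6) may also bring out delivery problems. This has some force, but the separation rests on opinion. The protocol labels only the two ends of the scale, so intermediate answers cannot be turned into lessons or hours. Focus groups reach some teachers and do not give delivery class by class.

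Finally, this is a feasibility measure on which no design figure depends. That is correct, and it limits the weight of the point.

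**Conclusion.** The concern holds in a limited form. Items 9 and 10 record no quantity. Reading them literally, and taking a lesson as a double session, their answers are the same for any number of halved lessons from one (92% of the planned time) to six (50%). Item 8 separates these cases only by self-rated adherence. Objective 3 therefore gets shares of teachers who agree, but no estimate of how much teaching was delivered.

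The plan's power and sample size are unaffected. The dilution figures rest on an assumed proportional relation and assumed shares of classes, so they are not evidence that teaching was or will be shortened. The change is worth making because it is cheap and serves a stated objective.

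**What to change.** In section 3.4.9:

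1. Define lesson, for example as one weekly session of two school hours.
2. Replace items 9 and 10 with three counts: how many of the six lessons were given (0–6), how many of these were shortened (0–6), and how many of the 12 school hours were taught in total (0–12). The lesson count must stay beside the hour count, because a teacher could fill 12 hours and still skip a lesson.
3. Keep item 8 as the teacher's own rating of adherence.
4. Report the distribution of lessons and hours delivered and the share of responding teachers who delivered all of them. Use this in aggregate when interpreting a null or small effect.

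An analysis relating each class's delivered hours to its pupils' outcomes needs more. A coded class identifier would have to be kept in the pupil data, where section 4.5 currently removes class membership, and the teacher form would have to carry the same code. The descriptive report in step 4 does not depend on this.

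**Cost.** Reworded items in the existing web form, with no new respondents or staff. Teachers' counts will carry some recall error. If the teacher questionnaires have already been completed, state the limitation when reporting fidelity.
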